**STUDY SUMMARY**

|                                       |   |
|---------------------------------------|---|
| Title                                 | The effect of multi-faceted intervention on osteoporosis and CKD-MBD  |
| Methodology                           | Prospective interventional cohort study   |
| Study Duration                        | Estimated duration for the main protocol is from January 1, 2020 to December 31, 2020.  |
| Study Center(s)                       | Multi-center (National Taiwan University Hospital and National Taiwan University Hospital Chu-Tung Branch)  |
| Objectives                            | To evaluate the effect of pharmacological therapy and behavioral interventions among patients with chronic kidney disease having risk of osteoporosis related fracture  |
| Number of Subjects                    | 60 subjects in a single arm   |
| Diagnosis and Main Inclusion Criteria | 
Inclusion criteria
 
 
1. Age > 50 years
 
2. CKD stage 3-4, and eGFR >20 mL/min/1.73m^2
 
3. FRAX® screening threshold: risk of hip fracture (HF) and major osteoporotic fracture (MOF) (HF: men> 6%, women > 7%; MOF: men> 15%, women> 12.5%)
 
 
Exclusion criteria
 
 
1. Unable to consent (e.g. dementia)
 
2. Have cancer under treatment
 
3. Have acute coronary syndrome (unstable angina, non-ST elevation myocardial infarction, ST-elevation myocardial infarction) or stroke in 3 months.
 
4. Limited cognitive or physical function for execute the intervention
 
 |
| Interventions                         | 
 
1. Pharmacological therapy for chronic kidney disease-mineral bone disorder and osteoporosis
 
2. Behavioral interventions including diet modification and exercise for bone and cardiovascular health
 
   |
| Statistical Methodology               | 
Primary outcome: all-cause mortality, cardiovascular events, subsequent fracture rate, and fall rate
 
Secondary outcome: biochemistry laboratory tests before and after multifaceted interventions
   |

## 1 STUDY OBJECTIVES

### 1.1 Primary Objective

- Collect the baseline characteristics to screen for CKD-MBD and osteoporosis among CKD patients/ Deliver optimal care including pharmacological therapy and behavioral interventions for CKD, CKD-MBD, osteoporosis, and fragility fractures accordingly to the baseline characteristics.
- Primary outcomes are all-cause mortality, cardiovascular events, subsequent fracture rates, and fall rate.

### 1.2 Secondary Objectives

- Secondary outcomes are changes of biochemistry laboratory data before and after interventions (pharmacological therapy and behavioral interventions).

## 2 BACKGROUND AND RATIONALE

### 2.1 Background on Condition, Disease, or Other Primary Study Focus

Previous studies among CKD patients found the fracture incidence to progressively increase by 15.0, 20.5, 24.2, 31.2, and 46.3 per 1000 person-years for CKD stages 1 to 2, 3a, 3b, and 4, respectively. The risk of fracture increases to 5 times higher in patients with an estimated glomerular filtration rate (eGFR) <15 versus >60 ml/min per 1.73 m^2). Patients with CKD and older than 65 years of age have a higher rate of fractures during 3-years of follow-up. It would be an important issue to prevent skeletal fracture among older adults with CKD since fracture can cause higher mortality and health resource utilization and loss of quality of life.

Renal osteodystrophy is used previously to describe the histological changes of bone among CKD patients. However, these changes in mineral and bone metabolism were derived from dysregulation during renal function deterioration gradually. Therefore, the mineral and bone disorder associated with CKD is an evolving entity which caused abnormalities of mineral metabolism, bone turnover, and vascular calcification. The KDIGO CKD-MBD guideline suggests that a bone biopsy should be considered for patients with a presentation of bone pain or unexplained fracture. A transiliac bone biopsy after tetracycline labeling is the gold-standard technique for diagnosis of CKD-MBD. However, this invasive measure might not be acceptable to many patients and only few centers have the expert histomorphometry analyzers. In clinical practice, the primary osteoporosis is a more prevalent disease among older adults. The KDIGO CKD-MBD also suggested application of dual-energy x-ray absorptiometry (DXA) in evaluation the fracture risk among CKD patients. In order to prevent fragility fracture, it would be reasonable to target abnormalities of mineral metabolism and primary osteoporosis. Further studies for CKD-MBD would be considered for those with unexplained fractures or bone pain. Tools to evaluate osteoporosis and CKD-MBD are briefly described below.

### **Bone mineral density (BMD)**

The relevance of bone mineral density as measured by dual-energy X-ray absorptiometry (DXA) is limited in CKD patients because of interference of scoliosis, osteoarthritis at the lumbar spine, and the presence of vascular or joint calcifications. However, BMD measurement was also recommended for older adults with CKD in the 2017 KDIGO guidelines which were supported by several studies.

### **FRAX®**

The Fracture Risk Assessment Tool can be used to predict peripheral fractures in older patients with CKD stages 2 to 5. Clinical risk factors such as weight, height, prevalent fracture, family history of hip fracture, and steroid use are sufficient for 10-year prediction and are as efficient alone as together with hip BMD.

### **Serum biochemistry**

#### **Vitamin D sterols.**

Circulating values of native vitamin D (25-hydroxyvitamin D [25OHD]) allow determination of vitamin D storage. But, the optimal circulating 25OHD level in CKD that protects against skeletal fractures is controversial. 2017 KDIGO guidelines recommend using the same 30 ng/ml cutoff value used for the CKD patient without dialysis.

#### **Phosphate.**

In previous study, serum phosphate levels are associated with higher fracture risk in both genders and in a subgroup of men with CKD. Tubular reabsorption of phosphate (TRP) in patients with CKD stage 3 to 4 is an index of phosphaturic homeostatic mechanisms.

#### **Parathyroid hormone.**

PTH is the best surrogate biomarker for bone histology in CKD in clinical practice.

Other biomarkers of mineral metabolism, such as calcium, and total ALP, are used as surrogate markers of high- or low-turnover bone disease.

#### **X-ray film.**

Lumbosacral spine anterior-posterior (AP) and lateral view will be used to evaluate aorta calcification and spinal compression fractures.

### **2.2 Study Rationale**

A prospective intervention study is purposed to investigate whether the optimal therapy targeting those with risk of fragility fracture risk and CKD would lead to the better outcomes. Patients with CKD stage 3-4 (eGFR 60-20mL/min/1.73m^2) are screened with FRAX®. If patients have high risk of osteoporotic fracture, they will be enrolled for serial examination and education to prevent complications of CKD and osteoporosis.

The primary outcomes are all-cause mortality, cardiovascular events, subsequent fracture rate, and fall rate. The secondary outcomes are changes of biochemistry laboratory data before and after interventions (pharmacological therapy and behavioral interventions).

### **3 STUDY DESIGN**

The design is a pilot study with data collection through interviews, and medical records. There is one study arm: the intervention. A description of multi-faceted intervention on osteoporosis and CKD-MBD can be found in STUDY INTERVENTIONS. The pilot will take place at two primary clinical care practices in National Taiwan University Hospital and its Chu-Tung Branch in Taiwan. 60 patients will be enrolled and followed for up from January 1, 2020 to December 31, 2020 with interviews and medical record reviews. Participants will undergo a baseline and follow-up interview to collect patient reported baseline and outcome measures.

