## **STATISTICAL CONSIDERATIONS**

### **9.1 Sample Size**

As this is a pilot study, we did not complete a formal sample size calculation. The chosen sample size is based upon the estimated number of patients that the funding supports their blood and urine examination, and bone density examination.

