### **9.2 Outcomes**

#### **9.2.1 Primary outcomes**

The primary outcome measures will be all-cause mortality, cardiovascular events, subsequent fracture rate, and fall rate from January 1, 2020 to December 31, 2020. The primary outcome measures will be collected during the baseline and follow-up (3-12 months) interviews in clinics.

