## 12 RESULTS

### 12.1 Number of Patients Screened

A total of 249 patients in outpatient clinic of two investigators were screened for osteoporosis risk assessment. If FRAX® screening criteria for Hip fracture risk: men with risk > 6%, women > 7% or major fracture risk: men > 15%, Women > 12.5% were reached. Those with exclusion criteria were excluded. Finally, from January 1, 2020 to December 31, 2020, 5 participants were enrolled for multifaceted interventions. After the intervention, 5 people had laboratory testing, bone density examination and health education during follow-up but no one completed the study. The study was terminated because of funding was only for one year. A total of 133 patients were screened in National Taiwan University Hospital, and a total of 116 patients were screened in Chu-Tung Branch, with an average age of 75.7 years. A total of 138 patients accounted for 55.4% of men. The average weight of men was 66.3kg, the average women were 57.3kg, and the average serum creatinine level 2.0 mg/dL for men and 1.8 mg/dL for women. The estimated glomerular filtration rate (eGFR) was 41.9ml/min/1.73m^2 for men and 38.1ml/min/1.73m^2 for women (Table 1). In the analysis of the reasons for exclusion, the highest was the lower risk of fractures estimated by FRAX® which accounted for 128 (51.4%), followed by failure to perform behavioral interventions (17.7%) and patients' refusal (15.7%).

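### The pilot label excuses a missing sample size calculation, but no feasibility outcome is pre-specified and Section 9.4 plans tests and regression that neither 60 nor 5 patients can support

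*Combined protocol and SAP*

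**What the plan says.** Section 3 describes the study this way: "The design is a pilot study with data collection through interviews, and medical records". It also says that "60 patients will be enrolled and followed for up from January 1, 2020 to December 31, 2020", and the Study Summary gives "60 subjects in a single arm". Section 9.1 explains the number: "As this is a pilot study, we did not complete a formal sample size calculation", and "The chosen sample size is based upon the estimated number of patients that the funding supports" for laboratory and bone density examinations.

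Section 9.2.1 states: "The primary outcome measures will be all-cause mortality, cardiovascular events, subsequent fracture rate, and fall rate". Section 9.4.2 makes laboratory results before and after the intervention the secondary outcome, and Sections 1.1 and 1.2 agree. None of these sections names recruitment, consent, visit attendance or completion as an outcome, or gives a criterion for going on to a larger study. The qualitative interview analysis in the assessments section (6.2.2) is not tied to any such outcome either.

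Section 9.4 plans descriptive statistics, then t-tests or Mann-Whitney tests, chi-squared tests, a paired t-test, and stepwise logistic regression with adjustment for confounders, all two-sided at 0.05. The Section 6.1 schedule has visits at months 3, 6, 9 and 12.

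Section 12.1 reports that 249 patients were screened and "5 participants were enrolled for multifaceted interventions". It says that none completed and that the study ended because funding covered one year only.

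**The concern.** A pilot can reasonably go without a power calculation if its purpose is to learn whether a larger study can be done. This plan takes the exemption without the purpose. It defines no feasibility quantity, no precision for one and no progression threshold, while its analysis section reads like that of a confirmatory or prognostic study.

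Two things are at stake. First, following Section 9.4 as written would give p-values and selected regression coefficients that rest on almost no events. Secondly, the recruitment figures, which are the most informative numbers the study has, appear only as post hoc description without intervals. The completion figure is open to misreading because of how the calendar was set.

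**Working it through.** **The planned size.** The 60 cannot be reproduced. No effect size, standard deviation, event rate, power or dropout is given, and Section 9.1 says that no formal calculation was done.

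**Expected fractures.** Section 2.1 gives rates from 15.0 to 46.3 per 1000 person-years. It lists five rates against four stage labels, so only the range is used. Expected fractures = patients × years × rate / 1000, with a full year of follow-up assumed for everyone:

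| Patients | at 15.0 | at 46.3 |
|---|---|---|
| 60 | 60 × 15.0/1000 = 0.90 | 60 × 46.3/1000 = 2.78 |
| 5 | 5 × 15.0/1000 = 0.08 | 5 × 46.3/1000 = 0.23 |

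Under a Poisson model, the chance of no fracture at all is exp(−0.90) = 41% to exp(−2.78) = 6% with 60 patients, and exp(−0.075) = 93% to exp(−0.23) = 79% with 5.

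Two assumptions pull in opposite directions:
- Entry spread evenly over the year would halve follow-up to 30 person-years, giving 0.45 to 1.39 fractures in 60 patients.
- A cohort selected for high fracture risk might exceed the quoted range. Doubling the top rate gives 60 × 92.6/1000 = 5.6.

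None of these counts supports stepwise selection among several covariates. With 5 patients the argument needs no rate: for any yes/no outcome, the smaller of the two groups has at most 2 people.

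**Paired laboratory comparison.** At two-sided 0.05 and 80% power (the power is an assumption), the paired t-test detects a standardized change of about 0.37 with 60 pairs and 1.68 with 5.

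**Recruitment, from Section 12.1.** The reported figures are consistent: 133 + 116 = 249 and 128/249 = 51.4%. Intervals are exact (Clopper-Pearson) 95%.
- Achieved against planned: 5/60 = 8.3%.
- Enrolled among screened: 5/249 = 2.0% (0.7% to 4.6%).
- Enrolled among those not excluded for low FRAX risk: 249 − 128 = 121, so 5/121 = 4.1% (1.4% to 9.4%). The 121 still includes people excluded for other reasons, so it is not the number eligible, which Section 12.1 does not give.
- Unexplained in the visible text: 17.7% of 249 is about 44 and 15.7% is about 39. If each person has one reason, 249 − 128 − 44 − 39 − 5 = 33 have none stated. Table 1 is not shown and may account for them.

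**Completion.** Enrolment and follow-up both run from 1 January to 31 December 2020. Counting back from 31 December, the month 3 visit needs entry by about the end of September, month 6 by the end of June, and month 9 by the end of March. Month 12 needs entry at the very start of January. The visible text does not give the enrolment dates of the 5. The exact interval for 0/5 would be 0% to 1 − 0.025^(1/5) = 52%, but the proportion does not measure retention unless the 5 could have reached month 12.

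**The case against.** The plan is open about its limits: Section 9.1 says how 60 was chosen and that nothing was calculated. Missing a recruitment target does not show that the target was an error, and judging it by Section 12.1 is hindsight. That stands. The absence of feasibility outcomes and the mismatch between size and analysis, however, can be seen without the results.

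Several stronger readings are tempting, and the documents do not support them:

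- A reader might infer that the study cannot report feasibility. Section 12.1 does so: numbers screened by site, main exclusion reasons, enrolment, non-completion and the reason for stopping. What is missing is pre-specification, targets and intervals.
- A reader might subtract all the named exclusions from 249 and conclude that the clinics could never have supplied 60. But 249 is the number screened, not a count of the eligible population. Refusers are not ineligible, and the reasons are not stated to be mutually exclusive.
- A reader might blame the shortfall on having only two clinics. Nothing in Section 12.1 links the two. It names one-year funding as the reason for stopping and low FRAX risk as the largest exclusion.
- A reader might say that the Section 9.4 tests cannot be run on 5 people. Section 12.1 says that all 5 had laboratory testing during follow-up, so a paired t-test on up to 5 pairs could be computed. It would be very weak, and at 60 it would have been a reasonable analysis.
- A reader might call all four primary outcomes rare. The documents give rates for fracture only.

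**Conclusion.** The concern holds in a limited form. The pilot label is used to omit a sample size calculation, no feasibility outcome or progression criterion is pre-specified, and the stepwise regression in Section 9.4 is not supportable. For fracture this is so at 60 (0.9 to 2.8 expected) as well as at 5 (0.08 to 0.23). For the other clinical outcomes it is certain at 5 and cannot be judged at 60, because no rates are given. The fracture counts rest on the Section 2.1 range applying to this cohort and on a full year of follow-up.

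The stated size was not delivered: 8.3% of plan, from a 2.0% screening yield. These are separate quantities and should be reported separately. The 0 of 5 completion largely reflects a study window that closed before nearly anyone could reach month 12, and it should not be read as poor retention.

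**What to change.** 1. **Size.** Keep the planned 60 in the Study Summary and Section 3, and state the achieved 5 beside it. Rewording 60 as a ceiling after the event would hide the shortfall.
2. **Feasibility.** Add eligible/screened, enrolled/eligible, visits attended, and completion among those whose entry date allowed them to reach each visit, all with exact 95% intervals. Take them from the screening log and visit records, and account there for the roughly 33 people without a visible reason. Label these estimates post hoc for this study and leave the stated primary and secondary outcomes in place. Making feasibility the primary outcome now would be a change made with the results known. Any successor should pre-specify these outcomes with progression criteria. Adherence is not on the list because no section says that it was asked about.
3. **Section 9.4.** Replace the bivariate tests and stepwise logistic regression with event counts, rates and paired laboratory changes, each with a confidence interval. Section 9.4 already plans descriptive statistics, so this is partly a deletion.

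The cost is protocol and SAP wording plus tabulation of existing records, with no new patients or data. The downside is that the clinical outcomes become descriptive and the reported size looks less favourable.

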### **4 SELECTION AND ENROLLMENT OF PARTICIPANTS**

Participants will be enrolled at two physicians in National Taiwan University and its Chu-Tung Branch. The intervention patient population will involve adults (age older than 50) with chronic kidney disease stage 3 or 4. Participants will be enrolled and identified using the inclusion/exclusion criteria. The physicians have been trained to conduct clinical trials.

#### **4.1 Inclusion Criteria**

1. Age > 50 years
2. CKD stage 3-4, and eGFR >20 mL/min/1.73m^2
3. FRAX® screening: risk of hip fracture (HF) and major osteoporotic fracture (MOF) (HF: men > 6%, women > 7%; MOF: men > 15%, women > 12.5% which were based on the result of previous studies in Taiwan).

#### **4.2 Exclusion Criteria**

1. Unable to consent (e.g. dementia)
2. Have cancer under treatment
3. Have acute coronary syndrome (unstable angina, non-ST elevation myocardial infarction, ST-elevation myocardial infarction) or stroke in 3 months.
4. Limited cognitive or physical function for execute the intervention

### **5 STUDY INTERVENTIONS**

#### **5.1 Interventions, Administration, and Duration**

The elicitation of goals will be embedded into clinical programs routinely offered to patients with chronic kidney disease. Research coordinator will be trained to

complete the interviews.

### **The core components of interventions**

- For participants with abnormal biochemical markers, pharmacological therapy and diet modification are applied.
- Dietary education on phosphorus additives is applied specifically for retention of phosphorus or high serum phosphorus level.
- Exercise for bone and cardiovascular health.
- Osteoporosis medications are initiated according to the reimbursed criteria of National Health Insurance, otherwise medications are used with non-insurance payment.

### **5.2 Handling of Study Interventions**

#### **Research coordinator**

The Research coordinator will be a trained health professional (e.g. nurse, dietitian, case worker).

#### **Responsibilities**

1. Undergo training and preparation to elicit and document patients' interview.
2. Remind the participants to visit clinic on schedule.

#### **Physicians**

The clinician will be a licensed health care professional (MD).

#### **Responsibilities**

1. Know or review patient's disease and care preferences.
2. Review, discuss, and update patient's health priorities on each visit.
3. Prescribe medications for chronic kidney disease and osteoporosis according to the results of blood and urine examination, and bone density.

## **6 STUDY PROCEDURES**

### **6.1 Schedule of Evaluation for Patient Population**

| Time period          | Screening | Informed Consent (Enrollment) | Clinic visit | Interviews (Patient Reported Outcomes) | Blood and Urine Examination | Bone density and Thoracolumbar x-ray film |
|----------------------|-----------|-------------------------------|--------------|--|-----------------------------|---|
| Enrollment (Day 1)   | x         | x                             | x            |  | x                           | x   |
| Follow-up Evaluation |           |                               | x            | x                                      | x                           |   |

|                                |  |  |  |  |  |  |
|--------------------------------|--|--|--|--|--|--|
| (3,6,9,12 th month) |  |  |  |  |  |  |
|--------------------------------|--|--|--|--|--|--|

## **6.2 Description of Research Assessments and Evaluations**

### **6.2.1 Screening Evaluation**

Potentially eligible patients will first be identified by administrative data within the Electronic Health Record (EHR). In the intervention arm, the primary care clinician will review the list and refer patients to a Research Coordinator at the practice who will be responsible for obtaining informed consent to participate in the trial. Interviews will be conducted primarily through the primary clinic. In the case that a potential participant does not meet the inclusion criteria or meet the exclusion criteria, they will be excluded. Participants in the trial will not receive payment.

### **6.2.2 Consent**

Although this study involves minimal risk, every effort will be made to ensure that all potential participants understand the details of the study. Additionally, it will be made clear that refusing to participate will not affect eligibility to receive services or benefits. Potential participants will be asked to demonstrate their understanding of what participation involves. If it is unclear that participants demonstrate full understanding of what is being asked of them, staff will continue the discussion until consent has been fully clarified.

### **6.2.2 Assessments and Data Collection**

For interviews, the result of questionnaire will be transcribed and transcripts will be coded by investigator of the research study. Qualitative interviews are analyzed using the constant comparative methodology. All coded material will be de-identified and aggregated for data analysis.

